The Video Interaction Guidance (VIG) programme is being implemented between March 2021 (with intake from July 2021) and June 2022 in four English Local Authorities (LAs). VIG is a relationship based parenting intervention in which a VIG practitioner films a parent and child interacting in short, one-to-one sessions. By providing feedback on these sessions based on edited clips of better than usual moments, VIG aims to promote parental sensitivity, child attachment and longer term social and emotional development.

The intervention developer, Babies 1st, will train and supervise 21 VIG Practitioners across the four LAs. Practitioners will undertake the role in addition to their substantive role (e.g. social or family worker) and will each work with a minimum of six families (typically a focal parent and infant dyad) over eight sessions or more.

The programme is being evaluated by IFF Research and the Policy Evaluation and Research Unit (PERU) at Manchester Metropolitan University (Man Met). The evaluation comprises impact, implementation (process) and cost components. The impact study design is a pragmatic, multi-site, effectiveness trial, with individual family dyads allocated to intervention and control within sites, at random, on a 1:1 intervention to control basis. Families allocated to the intervention group will receive VIG in addition to their usual care; those in the control group will receive usual care only. All families will be asked to complete a baseline questionnaire containing psychometric measures prior to randomisation and also at four months post-randomisation. In addition, LAs will supply child protection outcomes from administrative data six months post-randomisation.

Intake will begin in August 2021 and will continue until the end of March 2022. Randomisation will begin in July 2021, and the intervention for all families will end by June 2022. An evaluation report will be published by the end of August 2022.

The evaluation includes a review point (September 2021) to allow for changes to the protocol and evaluation activity on account of factors which are currently unknown (e.g., the amount of dropout and proportion of parents requiring translation services or additional support to complete the survey). For further details see p.12.

Table of Contents

Background and Problem Statement	6
Intervention and Theory of Change	6
Logic Model	9
Interventions	10
Mechanisms	10
Outcomes	10
Impact Evaluation	11
Research Questions	11
Design	12

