meeting, followed by three cycles of VIG and a final evaluation and feedback session. Each cycle consists of one session where the social worker films interactions between the parent and child and a Shared Review where the social worker highlights examples of positive interactions and encourages the parent to reflect on what they did well, what they can learn and how to replicate positive behaviour. Each session lasts around 45 minutes.

Logic Model⁴

⁴ Version 2

Interventions

The intervention will be delivered by 21 social and family workers in four local authorities. The social and family workers will be trained in VIG by Babies1st and the training will consist of an introductory training and follow-up workshop as well as fortnightly individual and monthly group supervision sessions, plus a Midpoint Review Day and Accreditation Day with external AVIGuk accredited trainers.

As part of their training, social and family workers have been supported to complete the VIG intervention with at least one 'pilot' family, under close supervision of a qualified VIG practitioner from Babies1st.

The intervention includes a minimum of eight sessions between the social and family worker and parent dyad, over the course of 3-4 months. The eight sessions consist of an initial introductory meeting, followed by three cycles of VIG and a final evaluation and feedback session. Each cycle consists of one session where the social and family worker films interactions between the parent and child and a Shared Review where the social and family worker highlights examples of successful interactions and encourages the parent to reflect on what they did well, what they can learn and how to replicate positive behaviour. Each session lasts around 45 minutes.

Mechanisms

During the Shared Reviews, the parent will be encouraged to reflect on themselves as a parent and the responsibilities that comes with this. They are also supported to be more aware of and reflect on their baby's needs. They will be encouraged to identify ways in which they are already responding sensitively to these needs, as well as opportunities to apply this positive behaviour to more stressful parenting situations.

The family and social worker supports the parent to celebrate and understand examples of sensitive parenting, encouraging the parent to feel proud of these moments.

Outcomes

It is hypothesised that the intervention will lead to the following short term outcomes:

- Higher parental self-esteem

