Once referral and consent procedures are complete, details of each dyad are passed to IFF Research, who check the completeness of the referral form data and confirm eligibility (that the dyad meets the study inclusion criteria). Subsequently, IFF administer a baseline questionnaire to the focal parent. The baseline questionnaire contains the following measures, details of which can be found in Appendix A: MORS-SF, Karitane Parenting Confidence Scale, Parental Stress Scale. For the sample randomised between July and November 2021, child protection outcomes (CiN, CPP, CLA and initiation of pre-proceedings) are collected from administrative case data held by the local authorities and further details provided later in this section. Full details of the measures included within the baseline questionnaire, along with the justification for their choice, and the reliance on self-completion questions rather than observations, is provided in the section entitled 'Outcome measures' below.

The respondent (focal parent) is expected to be the focal child's mother but may be the father where he is the only, or primary, care giver. Dyads are given two weeks to complete the questionnaire. It is important to note, that the study's funders have decided that all dyads that meet the study inclusion criteria and who provide their consent should be randomised, regardless of whether a complete baseline questionnaire is received. This means that some missing data, either item or unit (dyad) missing, can be expected at baseline. The evaluators in partnership with Babies 1st and the study sites will take a number of steps to limit non-response or missingness at baseline, such as telephone reminders to non-respondents, telephone support for focal parents to complete the questionnaire, and support for social workers and VIG Practitioners to support and encourage parents to participate.

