Once the period of time given to dyads to complete the baseline questionnaire has elapsed, IFF Research link the questionnaire return to the dyad's referral form data, pseudonymise the data and pass the data record to Manchester Metropolitan University (Man Met). A researcher based in Man Met's Policy Evaluation and Research Unit (PERU), who is blind to the identities of the dyads concerned will then randomise that dyad. Full details of the randomisation procedures are set out below. Once the dyad has been randomised, the outcome of randomisation is communicated by Man Met to IFF Research who in turn inform the Local Authority (LA) of the outcome. Following randomisation, LAs are free to commence work with dyads allocated to the intervention. It is expected that LAs will commence work with dyads very soon after randomisation so that the time between the end of the intervention and collection of post-intervention data is consistent across dyads. LAs should therefore only refer dyads for whom intervention delivery could commence immediately.

IFF Research will administer a follow-up questionnaire to all dyads (including those that did not supply a baseline questionnaire) five months following randomisation. Dyads will be given two weeks to complete the follow-up questionnaire. In large part, the follow-up questionnaire will contain the same or similar questions as the baseline questionnaire, and a similar set of procedures will be followed in order to limit attrition and missingness. IFF Research will seek a complete follow-up questionnaire from all randomised dyads, regardless of whether a dyad completed a baseline questionnaire.

At the end of the 'follow-up' fieldwork period, IFF Research will pseudonymise the follow-up questionnaire data and pass them to Manchester Met for analysis. Full details of the analysis are discussed below.

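### The co-primary outcomes are timed at four months in one section and five in another, and with intake to end March 2022 neither timing fits the end-August 2022 report

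*Protocol*

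**What the plan says.** **Follow-up time.** The Protocol Summary has families complete the questionnaire "prior to randomisation and also at four months post-randomisation". The Design section of the Impact Evaluation states: "IFF Research will administer a follow-up questionnaire to all dyads (including those that did not supply a baseline questionnaire) five months following randomisation". Both are current text. The questionnaire supplies MORS-SF warmth and invasion (co-primary) and the two self-report secondary scales.

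**Response windows.** At follow-up: "Dyads will be given two weeks to complete the follow-up questionnaire". At baseline: "Dyads are given two weeks to complete the questionnaire". Randomisation comes after the baseline window: "Once the period of time given to dyads to complete the baseline questionnaire has elapsed", the record is linked and passed on for allocation.

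**Calendar.** From the Summary: "Intake will begin in August 2021 and will continue until the end of March 2022", and "An evaluation report will be published by the end of August 2022". The Summary also ends delivery for all families by June 2022. The Interventions section describes the sessions as taking place "over the course of 3-4 months".

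**Who is followed, and when data move.** The Design section seeks a follow-up questionnaire from every randomised dyad and passes the data to the analysts once follow-up fieldwork has closed.

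**A timetable limit for one outcome only.** The Design section and the step-up paragraph under Outcome Measures restrict the step-up outcome to dyads randomised from July to November 2021, so that six months can elapse within the project. No such limit is stated for the questionnaire outcomes.

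**The concern.** Fieldwork can follow only one date. With two in the protocol, the co-primary outcomes have no defined assessment time, and an analysis plan written later cannot repair a survey already sent at the wrong month. The protocol itself treats this timing as important: it asks local authorities to start work promptly so that the gap between the end of the intervention and data collection is similar for all dyads.

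The second difficulty is the calendar. The promise to follow every randomised dyad, the end-March close of intake and the end-August report do not obviously fit together under either follow-up time. The authors dealt with this constraint for the step-up outcome but not for the outcomes on which the trial will be judged. If the dates are left as they are, someone will have to decide during the trial whether to delay the report or analyse without the latest dyads, and the protocol gives no rule for that decision.

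**Working it through.** The check is calendar arithmetic.

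**Inputs**
- End of intake: 31 March 2022 (Summary).
- Follow-up: 4 months (Summary) or 5 months (Design).
- Follow-up response window: 14 days (Design).
- Baseline window before randomisation: 14 days (Design).
- Report due: 31 August 2022 (Summary).
- Total 252 dyads; about 150 randomised July to November 2021 (Secondary Analysis).

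**The plan's own calendar for step-up.** 30 November 2021 + 6 months = 30 May 2022, well before the report. That restriction does what it is meant to do.

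**The same check for the questionnaire.** Window close = last randomisation + follow-up months + 14 days. The end of intake can be read in two ways: (a) the last randomisation is on 31 March; (b) the last referral is on 31 March, so randomisation falls on 31 March + 14 days = 14 April.

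| Follow-up | Reading | Sent | Window closes | Relative to 31 August 2022 |
|---|---|---|---|---|
| 5 months | (a) | 31 August | 14 September | 14 days after |
| 5 months | (b) | 14 September | 28 September | 28 days after |
| 4 months | (a) | 31 July | 14 August | 17 days before |
| 4 months | (b) | 14 August | 28 August | 3 days before |

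**Number of dyads past the deadline at five months.** The last randomisation whose window closes by the report date is 31 August − 14 days − 5 months = 17 March 2022, with no time left for analysis.
- Dyads still to come after November: 252 − 150 = 102.
- Reading (a), spread evenly over December to March (31 + 31 + 28 + 31 = 121 days): 102/121 = 0.84 per day. From 18 to 31 March is 14 days, so 14 × 0.84 = 11.8, about 12 dyads; 12/252 = 4.8%.
- Reading (b), the same 102 spread to 14 April (135 days): 102/135 = 0.76 per day. From 18 March to 14 April is 28 days, so 28 × 0.76 gives about 21 dyads (8%).

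**Illustration with an assumed data lock.** The protocol gives no lock date. Suppose it were 15 July 2022, and take reading (a) at 102/4 = 25.5 dyads per month.
- Five months: 15 July − 14 days − 5 months = 1 February. Two months of accrual fall outside: 2 × 25.5 = 51 dyads.
- Four months: 15 July − 14 days − 4 months = 1 March. One month falls outside: about 25 dyads.

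**Delivery dates.** A course starting on 31 March 2022 and lasting three months ends on 30 June, which agrees with the Summary. One lasting four months ends on 31 July, which does not. The conflict exists only at the upper end of the 3-4 month range.

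**The case against.** The case on the other side concerns size and consequence, since the contradiction and the dates are plain.

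- **The direct overrun is small.** On the stated dates with randomisation ending on 31 March, about 12 dyads are affected. This stands. It limits the harm but does not remove the need for a single time point.
- **A reader might infer a large loss of sample and power,** for instance by taking the step-up restriction to imply a late-May data cut for the surveys too. The documents do not support this. The restriction is explained by the six-month window for administrative data, and no survey cut-off is stated. The minimum detectable effect does not depend on follow-up length, and any reduced sample would rest on a lock date that the reader supplies.
- **A reader might infer that late dyads will be surveyed early or dropped.** As written, every dyad is surveyed at the stated month. The conflict is with the report date.
- **A reader might infer that a four-month survey mixes measurements taken during and after the intervention.** This is possible if delivery takes the full four months or starts late. However, the stage 2 qualitative section speaks of a three-month intervention, and the Design section expects work to start very soon after randomisation. The extent of any overlap cannot be quantified from the protocol.
- **The Timeline chart might close recruitment earlier.** Its cells cannot be read reliably in the text available. If intake ended on 28 February 2022, a five-month window would close on 11 August. The chart would then disagree with the Summary, which is a further reason to reconcile the dates.

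**Conclusion.** The point holds. The assessment time of both co-primary outcomes is stated as four months in one section and five in another, and the protocol does not show which is intended. At five months, follow-up of the last dyads closes 14 to 28 days after the report is due. At four months it closes 3 to 17 days before, which is too little for linkage, multiple imputation, bounds, bootstrapping and reporting.

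The size is modest. About 12 of 252 dyads (5%) cannot close five-month follow-up by the report date. This assumes 150 randomised by November, even accrual afterwards and a last randomisation on 31 March; the referral reading raises it to about 21. Leaving time for analysis would raise it further, but by how much depends on a lock date that has to be assumed. For a mid-July lock the figures are about 25 dyads at four months and about 51 at five. No claim about lost power follows from the documents. The correction is still needed before fieldwork, because the endpoint is undefined without it.

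**What to change.** 1. State one follow-up time and use it in both the Summary and the Design section.
2. Say whether the end-March 2022 date is the last referral or the last randomisation.
3. State a data-lock date for the questionnaire outcomes, and align the last randomisation, the close of follow-up and the report date with it. The simplest way is to move the lock and the report to after the last response window closes. The alternative is to end intake early enough for every dyad to complete follow-up before the lock.
4. Reconcile the end-March intake with delivery ending by June 2022 and a delivery period of up to four months, and check the Timeline chart against the agreed dates.

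The cost is protocol wording plus either a short delay to the report or a slightly earlier close of intake with somewhat fewer dyads. No new procedures or data are needed.

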Randomisation	14
Participants	15
Sample Size / Minimum Detectable Effect Size Calculations	16
Outcome Measures	18
Analysis Plan	20
Primary Analysis	21
Secondary Analysis	24
Exploratory Analysis	25
Contextual Factors Analysis	25
Implementation and Process Evaluation	26
Aims	26
Research Questions	26
Design	26
Methods	27
Analysis	30
Cost Evaluation	31
Risks	33
Ethics & Participation	34
Registration	34
Data Protection	34
Personnel	36
Timeline	40
Appendix A: Scales used in baseline and follow-up questionnaires	41

Background and Problem Statement

Problem Statement

There were 399,500 children in need on 31st March 2019 in England (ONS, March 2019), and 19,489 of them were under one year old.

Parents who have themselves been neglected and abused will frequently struggle to tolerate their babies' cries and interpret them in a realistic and benign manner. Babies' vulnerabilities may evoke in parents their own unconscious experiences of being looked after. If parents have experienced harsh parenting, parents may be prone to replicate this pattern of behaviour.

The first twelve months of a child's life provide a 'window of opportunity' to increase parental sensitivity, reduce risk and support changes in parenting styles, leading to changes in the trajectory of parent-infant relationships, infant speech development, school readiness, and other life outcomes.

The aim of the VIG programme is to improve the practice of social workers and family workers to make a difference to the lives of vulnerable families and give parents and their babies a genuine chance for a better start in life.

Intervention and Theory of Change

Brief name: Empowering Parents and Professionals Using Video Interaction Guidance (VIG) programme (Babies1st)

Why: Parents who have themselves been neglected and abused will frequently struggle to tolerate their babies' cries and interpret them in a realistic and benign manner. Babies' vulnerabilities may evoke in parents their own unconscious experiences of being looked after. If parents have experienced harsh parenting, parents may be prone to replicate this pattern of behaviour. The aim of the programme is to support families with a child under 12 months who is the subject of a Child in Need (CiN) or Child Protection (CP) Plan through the use of Video Interaction Guidance (VIG) in order to improve parental self-esteem and confidence, to enhance parental reflective functioning, capacity to mentalise, and lower parental stress.

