The impact study design is a pragmatic, multi-site, effectiveness trial, with parent-infant dyads allocated to intervention and control within sites, at random, on a 1:1 basis. As a result, dyads are randomised within sites, which are local authorities, and the resulting data are clustered by site. Outcomes are recorded for the focal parent and focal child within dyads. There are four sites in total, with family dyads identified within each site by local intervention coordinators and then randomised to treatment and control using a randomised permuted block approach described more fully below.

Trained social workers are responsible, after training and discussions with Babies 1st, for identifying all eligible dyads that meet the inclusion criteria (with the exception of those for whom exclusion criteria apply), completing a referral form for each dyad and administering consent procedures. The referral form contains the following information:

- Focal parent’s contact details
- Focal parent’s age
- Focal child’s age
- Focal child’s gender
- Focal child subject to formal multi-disciplinary planning process (i.e. CP, CiN, Early Help Plan)?
- Other children in the household subject to formal multi-disciplinary plan?
- Ethnicity
- Focal parent’s care history
- Focal parent has other children taken into care?
- Does the focal parent smoke?

- Current accommodation
- Age focal parent finished full-time education
- Focal parent currently suffers from anxiety
- Focal parent currently suffers from depression
- Focal parent's alcohol consumption

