The participants in this study are families (expected to be represented mostly mother-baby dyads) within four English local authorities (LAs), recruited using convenience sampling. Formal expressions of interest were originally received from five LAs, and partnerships with four LAs meeting all eligibility criteria were finalised by mid-March 2021. Babies1st then trained social and family workers in each LA to become VIG Practitioners, assuming that each practitioner would work with around six dyads.

Table 2: Dyad recruitment and VIG practitioner numbers by site

Local Authority	Dyads recruited	VIG Practitioners
Achieving for Children (AfC)	120	10
Bath and North-East Somerset (BANES)	24	2
London Borough of Hounslow	24	2
Stockport	84	7

Criteria for including families in the study have been determined by local authorities in conjunction with Babies 1st, and are as follows:

- The family has a focal child aged 12 months or less; and
- The focal child is subject to either a Child in Need plan (CiN) or a Child Protection plan (CPP)

Families meeting these criteria will be eligible for inclusion unless they meet one or more of the following exclusion criteria:

- The focal parent does not speak or read English and does not have access to an interpreter (though this will be reviewed in September 2021 and the criteria may change);
- The referring social worker believes there to be a reason why the parent(s) cannot manage a psychological intervention at time of referral, due to:
 - serious mental health concerns;
 - serious physical health concerns;
 - being actively engaged in substance misuse.

Translation of the questionnaire instruments and provision of an interpreter for respondents who do not speak or read English were not planned due to budgetary constraints because VIG is primarily delivered in English. Furthermore the instruments the evaluation is using to measure the primary and secondary outcomes are not validated for the full range first languages spoken by parents. However, in September 2021 this will be reviewed following initial programme intake and through discussions with LAs. If there is a need for translations they will be undertaken.

Sample Size / Minimum Detectable Effect Size Calculations

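### Earlier VIG is neither excluded nor flagged, and no field shows whether a dyad's worker is VIG-trained, so control exposure is possible and the MDES makes no allowance for it

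*Protocol*

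**What the plan says.** **Earlier VIG.** The Interventions section states that "The intervention will be delivered by 21 social and family workers in four local authorities" and that in training "social and family workers have been supported to complete the VIG intervention with at least one 'pilot' family, under close supervision". Under Participants, a family qualifies through the child's age (12 months or less) and a Child in Need or Child Protection plan, and then: "Families meeting these criteria will be eligible for inclusion unless they meet one or more of the following exclusion criteria". The exclusions are lack of English without an interpreter, and the referring worker's view that the parent cannot manage a psychological intervention because of serious mental or physical ill health or active substance misuse. The shorter eligibility statement under Sample and Recruitment adds nothing on earlier VIG. The itemised referral form in the Design section has no field for it, and none for the identity or training of the allocated worker.

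**Who works with whom.** The Summary says: "Practitioners will undertake the role in addition to their substantive role (e.g. social or family worker". The Design section says: "Trained social workers are responsible, after training and discussions with Babies 1st, for identifying all eligible dyads that meet the inclusion criteria". The Risks table notes that families in both arms all have a social worker. The Problem Statement says: "The aim of the VIG programme is to improve the practice of social workers and family workers".

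**Safeguards.** The Analysis Plan recognises that some controls may receive VIG, but only by mistake or circumvention. Secondary Analysis would seek exposure records in both arms where this can be done, and a complier analysis if they are good enough. The Cost Evaluation assigns monitoring of usual care in each authority to the process evaluation. The sample size section assumes near-complete compliance and plans to check it among intervention dyads.

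**The concern.** The primary questions compare VIG with business as usual. Two ordinary features of delivery could narrow that contrast without anyone breaking a rule.

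First, a training family whose baby is still 12 months or less and on a plan meets every stated criterion. If allocated to control, it has already had VIG. If allocated to intervention, it is being treated again. The evaluator's eligibility check works from the referral form, so it could not see this.

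Second, a control dyad's own worker may be one of the 21 practitioners. The programme aims to improve workers' practice, and the logic model lists better ability to support service users among its effects. Some of that could reach control families in everyday casework.

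At stake are the size of the intention-to-treat difference and how a small or null difference is read. Eligibility rules and pre-randomisation fields must be settled before enrolment. A later analysis plan cannot supply them.

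**Working it through.** **1. Reproduce the stated MDES.** Inputs from the sample size section: R² = 0.50, two-sided alpha 0.05, power 0.80, 1:1 allocation and a harmonic mean site size of 21. From the last column of Table 3, the harmonic mean of 67, 47, 13 and 13 is 21.05. With four sites the effective N is 4 × 21 = 84, and df = 84 − 6 = 78.

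MDES = (t₀.₉₇₅ + t₀.₈₀) × √[(1 − R²) / (0.25 × N)] = 0.438 at N = 84, which agrees with the stated 0.44. The same formula with all 141 completed cases gives 0.336, so the protocol's figure is conservative. Neither calculation contains a term for control exposure.

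**2. Ceiling on pilot re-entry.** With one family for each of 21 practitioners, 21 / 252 = 8.3% of dyads if every one re-entered. One per practitioner is the stated minimum, so this ceiling is itself an assumption. Re-entrants would be split between the arms by randomisation. Assuming they gain nothing further from VIG, a 0.44 SD effect averages 0.44 × (1 − 0.083) = 0.403 SD. If a quarter re-entered, the share is 2.1% and the average 0.431 SD.

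The age rule limits this further. Authority partnerships were finalised by mid-March 2021 and training followed. Recruitment opens in mid-July, four months later. A baby older than about 8 months in mid-March would be past 12 months by then. Younger babies could still qualify.

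**3. Spillover through workers.** The documents give neither the share of controls with a VIG-trained worker nor the fraction of effect passed on. For illustration only, take 10–40% of controls and half the effect:

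- 0.10 × 0.5 = 5% dilution: 0.44 × 0.95 = 0.42 SD
- 0.40 × 0.5 = 20% dilution: 0.44 × 0.80 = 0.35 SD

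**4. Consequence for power** (normal approximation, residual SD √0.50, true effect 0.44 SD):

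| Dilution | ITT effect (SD) | Power, 84 cases | Power, 141 cases |
|---|---|---|---|
| 0% | 0.440 | 0.81 | 0.96 |
| 5% | 0.418 | 0.77 | 0.94 |
| 10% | 0.396 | 0.73 | 0.91 |
| 20% | 0.352 | 0.63 | 0.84 |

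The undiluted effect needed for 80% power, MDES / (1 − dilution), rises from 0.438 to 0.461 (5%) and 0.547 (20%) with 84 cases. With 141 cases it rises from 0.336 to 0.354 and 0.420.

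**5. Do the planned safeguards reach these routes?**

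- Exposure records are conditional and concern receipt of the programme. They might pick up a former pilot family, but not a worker using VIG skills with a control family.
- Usual-care monitoring is promised, yet the process evaluation's design table has no usual-care or control-arm indicator. Its 24 parent interviews are spread across VIG practitioners after the intervention, so they reach treated families.
- The compliance review looks at the intervention arm only.

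**The case against.** The strongest reply is that all of this is possibility. Nothing says that a pilot family was referred or that any control dyad's worker is a practitioner. The protocol often names social workers and VIG practitioners as separate groups, the Design section also has local coordinators identifying dyads, and referrers need not be among the 21. VIG itself is filming, clip selection and shared review, which ordinary casework does not deliver by accident. An authority that knows a family has had VIG may simply not refer it. All of this stands, and it is why no rate can be given.

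A reader might infer that VIG does carry over into usual care unrecorded and that the contrast is diluted. The documents do not support this. Exposure records are planned for both arms, though conditionally, and usual-care monitoring is assigned. Earlier VIG is a pre-randomisation characteristic that would fall in both arms, so it is not leakage into control alone, nor does it break the randomised comparison. It can only lower the average effect among those enrolled. The baseline MORS-SF in equation [1] would take up part of any earlier gain, but it cannot restore a contrast if repeat treatment adds little.

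A reader might also infer that a null result would be uninterpretable. That is too strong for dilution of 5–20%: with 141 cases, power for 0.44 SD stays near 84% even at the upper end.

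Exposure coding could be left to an analysis plan. The exclusion and the referral fields could not.

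**Conclusion.** The point holds as a gap in design. The protocol does not exclude or identify focal parents already treated with VIG. It does not separate VIG-trained workers from control dyads or record where they overlap. Control exposure through ordinary working is therefore possible, would be only partly visible in the planned records, and is absent from the MDES.

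Its size is unknown. The 8% figure is a ceiling that assumes one pilot family per practitioner and full re-entry. The 5–20% dilution rests on assumed shares and an assumed half-effect transfer. Within that range the power loss is moderate: from 0.81 to 0.77–0.63 on the protocol's 84-case basis, or from 0.96 to 0.94–0.84 with 141 cases. The change is worth making because it is cheap and the information is hard to rebuild afterwards, not because dilution has been shown.

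**What to change.** - **Participants:** exclude focal parents who have previously received VIG, including as a training pilot family. Align the eligibility statement under Sample and Recruitment.
- **Design, referral form:** add two yes/no fields, completed before randomisation: whether the focal parent has had VIG before, and whether the dyad's allocated worker is one of the 21 VIG practitioners.
- **Sensitivity analysis – primary outcomes:** repeat equation [1] in dyads whose pre-randomisation worker is not a VIG practitioner, and report it beside the main estimate. The field is fixed before allocation, so both arms are restricted alike and the comparison stays randomised.

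**Cost.** A few dyads would be lost to the exclusion, and the restricted sample would be smaller. If 10–40% of dyads were set aside (an assumption), standard errors would grow by a factor of 1/√0.9 = 1.05 to 1/√0.6 = 1.29. Later changes of worker would not be captured. The restricted estimate also describes a narrower group, so a difference from the main result would suggest dilution without proving it.
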